8.4.8. AEs of Clinical Interest

8.4.8.1. Infusion/Injection-Related Reactions

All therapeutic proteins can elicit immune responses, potentially resulting in hypersensitivity or allergic reactions such as rash, urticaria, angioedema, serum sickness, and anaphylactoid or

anaphylactic reactions. As with any SC or IV injection, infusion/injection-related reactions can occur during or after administrations. Overall, the frequency of injection-related reactions in clinical studies has been low.

Refer to the current efgartigimod IB for more information on infusion/injection-related reactions.

8.4.8.2. Injection Site Reactions

An injection-site reaction is any AE developing at the injection site. Localized injection site reactions are frequently observed in studies in which efgartigimed is comixed with PH20 and administered SC. The most frequently reported injection-site reaction AEs are *Injection site erythema*, *Injection site pain*, and *Injection site swelling*.

Any injection-site reaction will be reported as an AE (Section 8.4). Certain types of local reactions could be photographed and shared with the sponsor for review and assessment.

As a routine precaution, participants will be trained or observed closely by a trained health care professional for any potential injection-site reaction.

Refer to the current IB for more information on injection site reactions.

8.5. Pharmacokinetics

Blood samples for PK analysis will be collected from each participant as described in the SoA (Table 1). Samples will be collected predose on IMP administration visits (within ≤2 hours before IMP administration) and any time if no IMP is administered. During unscheduled visits, blood samples for PK will be collected only if IMP is administered.

In part A only, 1 additional PK sample will be collected from at least 28 participants on day 10 (±1 day; should be collected at least 2 days after the second IMP dose is administered at week 1).

Efgartigimod serum concentrations will be determined using a validated assay.

The actual date and time of collection of each blood sample will be recorded in the requisition form. If no sample is taken, the reason will be recorded in the relevant section of the eCRF.

8.6. Pharmacodynamics

Blood samples will be collected for the determination of PD markers (total IgG serum levels, anti-BP180 and anti-BP230 antibodies, and _______) as described in the SoA (Table 1). Total IgG serum levels, anti-BP180 and anti-BP230 antibodies, and ______ will be quantified at a central laboratory, and results will only be reported to investigative sites or other site staff at screening, to maintain study blind.

For baseline and all postbaseline PD assessment time points (Table 1), sample collection will be performed predose at IMP administration visits (within ≤2 hours before IMP administration). PD markers will be determined using validated assays.

The actual date and time of collection of these blood samples will be recorded in the requisition form. If no sample is taken, the reason will be recorded in the relevant section of the eCRF.

PD blood samples that are collected at the screening visit may be used for methodology validation and/or for future research purposes (Section 8.3.6.3). Such use of these samples

is only permitted after obtaining consent from the participant; this is described further in the ARGX-113-2009 ICF.

8.7. Genetics

Not applicable to ARGX-113-2009.

8.8. Biomarkers

Not applicable to ARGX-113-2009.

8.9. Immunogenicity Assessments

Blood samples will be collected to assess the serum levels of antidrug antibodies (ADA) against efgartigimed and plasma levels of antibodies against rHuPH20 as indicated in the SoA (Table 1). Samples will be collected predose on IMP administration visits (within \leq 2 hours before IMP administration).

All samples will be analyzed in a 3-tiered approach using validated immunogenicity methods. First, all samples will be evaluated in a screening assay (tier 1) and scored as positive or negative. Second, screened positive samples will be evaluated in a confirmatory assay to assess the specificity of the immunogenicity response. The samples will be scored as confirmed positive or confirmed negative. Samples confirmed positive in tier 2 will be further analyzed in a titration assay to characterize the magnitude of the antibody response and a neutralizing antibody (NAb) assay to assess the antibodies for neutralizing activity.

The actual date and time of collection of these blood samples will be recorded in the requisition form. If no sample is taken, the reason will be recorded in the relevant section of the eCRF.

Immunogenicity blood samples that are collected at the screening visit will only be used for methodology validation and/or for future research purposes (Section 8.3.6.3). Such use of these samples is only permitted after obtaining consent from the participant; this is described further in the ARGX-113-2009 ICF.

8.10. Imaging Substudy

A photography substudy will be performed at selected study sites. In this substudy, site staff will take photographs of bullous lesions located at various anatomical regions of participants per the discretion of the investigator. As a guidance, time points of baseline, CDA, CR, and relapse are indicated; however, photographs may also be taken at intermediate time points.

Photography is generally accepted as a routine practice for documenting dermatological conditions in medicine. Participants will be requested to provide consent for any use that will be made of the image and for sharing anonymized pictures with the sponsor.

8.11. Health Economics OR Medical Resource Utilization and Health Economics

Not applicable to ARGX-113-2009.

9. STATISTICAL CONSIDERATIONS

The SAP will be finalized before the interim and final database lock of part A and the final database lock of part B, and it will include a more technical and detailed description of the statistical analyses described in this section. The below paragraphs contain the main general features of the statistical analysis.

9.1. Statistical Hypotheses

Part A:

The main goal of part A is to determine whether efgartigimod PH20 SC is effective in the treatment of participants with BP via assessment of the study's primary endpoint: the proportion of participants who are in CR while receiving efgartigimod PH20 SC or placebo and have been off OCS therapy for ≥8 weeks at week 36. Thus, the null hypothesis to be tested in relation to the primary endpoint of part A is as follows:

• Null hypothesis: efgartigimod PH20 SC is not different from placebo with respect to the achievement of CR while receiving efgartigimod PH20 SC or placebo and having been off OCS therapy for ≥8 weeks at week 36.

Part B:

The primary objective of part B is to demonstrate that efgartigimod PH20 SC is superior to placebo in achieving CR while receiving efgartigimod PH20 SC or placebo and having been off OCS therapy for ≥8 weeks at week 36. Thus, the null hypothesis to be tested in relation to the primary estimand (part B) is as follows:

• Null hypothesis: efgartigimod PH20 SC is not different from placebo with respect to the achievement of CR while receiving efgartigimod PH20 SC or placebo and having been off OCS therapy for ≥8 weeks at week 36.

The null hypotheses corresponding to the estimands for the proposed key secondary endpoints of part B (Table 4) are as follows:

- 1. Efgartigimod PH20 SC is not different from placebo with respect to the cumulative dose of OCS from baseline to week 36.
- 2. Efgartigimod PH20 SC is not different from placebo with respect to the proportion of participants who achieve an IGA-BP score of 0 while receiving efgartigimod PH20 SC or placebo and have been off OCS therapy for ≥8 weeks at week 36.
- 3. Efgartigimod PH20 SC is not different from placebo with respect to the proportion of participants who achieve CDA while receiving efgartigimod PH20 SC or placebo and remained free of relapse through week 36.
- 4. Efgartigimod PH20 SC is not different from placebo with respect to the proportion of participants in CR while receiving efgartigimod PH20 SC or placebo and receiving minimal OCS therapy for ≥8 weeks at week 36. (Minimal OCS therapy is defined as ≤0.1 mg/kg/day of prednisone or an equivalent dose of another OCS].)
- 5. Efgartigimod PH20 SC is not different from placebo with respect to changes from baseline in the 24-hour average itch score from the Itch NRS.

9.1.1. Multiplicity Adjustment

For part B of the study, the statistical comparisons for the primary endpoint and the key secondary endpoints will be carried out in the hierarchical order as indicated above. However, after interim analysis of part A data, another multiplicity adjustment testing strategy (eg, Holm's multiplicity adjustment) might be put forward if appropriate. The proposed hierarchical approach implies that statistically significant results for the comparison in the higher rank (primary, then ranked key secondary variables) are required to initiate the testing of the next comparison in the lower rank. Because a fixed-sequence procedure is used, each comparison will be tested at a significance level of 0.05 and an overall alpha level of 0.05 will be preserved.

9.2. Analysis Sets

Table 8 lists and defines the analysis sets to be applied in this study.

Table 8: Analysis Sets for ARGX-113-2009

Participant Analysis Set	Description
Full analysis set	All randomized participants. Participants will be included in the analyses according to the study arms to which they were randomized.
Safety analysis set	All randomized participants who received at least 1 dose of IMP. Participants will be analyzed according to the intervention they actually received.
Per protocol analysis set	All full analysis set participants who did not have a major protocol deviation impacting the efficacy results. The determination of the per protocol population will be finalized and documented before database lock and unblinding.

IMP=investigational medicinal product

The full analysis set is used to analyze endpoints related to the efficacy objectives and the safety analysis set is used to analyze the endpoints and assessments related to safety. Sensitivity analysis for efficacy will be performed in the per protocol analysis set.

9.3. Statistical Analyses

9.3.1. General Considerations

In general, data collected will be listed, together with derived variables. Descriptive statistical methods will be used to analyze safety and efficacy data. Summaries will generally be provided by treatment assignment and overall.

Summaries for continuous measures will include the number of observations (n), mean, SE, median, minimum and maximum. For categorical variables, summaries will include sample size, frequencies, and percentages.

The baseline value will be the last assessment before the first administration of IMP.

All study visits will be recalculated based on actual dates and will be referred to as "analysis visits" which will be used in the statistical analyses. The rules for calculating the analysis visits will be documented in the SAP. Rules for imputing partial dates or missing dates will also be documented in the SAP.

9.3.2. Primary Endpoint/Estimand Analysis

The estimand framework for analysis of the primary endpoint applies only to part B of this study.

- Population: adult participants with newly diagnosed or relapsing BP, regardless of whether the participant is naïve to treatment or has previously received treatment. Participants will be receiving concurrent therapy of oral prednisone (or equivalent OCS); therefore, candidates who have a known contraindication to OCS will be excluded from study participation (exclusion criterion 4).
- Variable: proportion of participants who are in CR while receiving efgartigimod PH20 SC or placebo and have been off OCS therapy for ≥8 weeks at week 36.
- Main intercurrent events (ICE):
 - 1. Intercurrent treatments before week 36
 - a. Immunosuppressants or dapsone at a therapeutic dose for at least 4 weeks
 - b. IVIg/SCIg at an immunomodulating dose (at least 1 g/kg/month)
 - c. Tetracyclines at therapeutic dose for at least 2 weeks
 - d. Rituximab or anti-CD20 biologic, at least 1 infusion
 - e. Plasma exchange or immunoadsorption, at least 1 procedure
 - f. IV or IM corticosteroids administered in the following conditions:
 - At least 1 administration, any dose, from week 28 to 36 (ie, during the 8-week period required to confirm CR off OCS therapy)
 - At any time before week 28 in any of the 3 following situations:
 - More than 60 mg/day of prednisone or prednisone equivalent dose for 3 consecutive days
 - More than 40 mg/day of prednisone or prednisone equivalent dose for 4 consecutive days
 - o More than 7 days in total
 - g. Any interventional study drugs under development for BP
 - h. Very potent TCS with a weekly dose >20 g for 1 week
 - 2. Discontinuation of IMP before week 36 due to lack of efficacy

Population-level summary: the odds ratio (95% confidence interval [CI]) under efgartigimod PH20 SC in combination with concurrent OCS therapy versus placebo in combination with concurrent OCS therapy.

Handling of main ICEs: a composite strategy approach will be taken to address both main ICEs. This implies that participants who take intercurrent treatments and participants who discontinue IMP due to lack of efficacy will be considered nonresponders for the primary endpoint analysis.

Handling of missing data:

- Missing data for reason of 1 of the main ICEs will be handled as described above.
- If CR information is missing for the primary endpoint, the participant will be considered a nonresponder. Further details on other imputation techniques for missing CR information will be provided in the SAP.
- Details on handling other missing data will also be provided in the SAP.

Final analysis model: the proportion of participants with BP who are in CR while receiving efgartigimod PH20 SC or placebo and have been off OCS therapy for ≥8 weeks at week 36 will be tested using a Cochran-Mantel-Haenszel (CMH) test stratified for the 2 stratification factors of disease history (newly diagnosed versus relapsing) and disease severity (moderate versus severe). The odds ratio will be provided, along with the 95% CI and 2-sided p-value.

Supplementary analyses: to facilitate interpretation of the estimated treatment effect in the primary analysis, supplementary analyses will be conducted on the supportive estimand where the main ICEs are handled differently (eg, by using the hypothetical or treatment policy strategy instead of composite strategy). Details will be provided in the SAP.

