2.1. Study Rationale

BP is a subepidermal autoimmune blistering disease (AIBD) that predominantly affects older adults. It is a chronic disease that significantly impacts morbidity and QoL; additionally, the disease can worsen spontaneously, even when the patient is treated with the current standard of care. The pathogenesis of BP is driven by IgG and IgE autoantibodies against the hemidesmosomal proteins BP180 and BP230, acting as key antigens for pathogenic autoantibodies. These pathogenic autoantibodies are understood to directly interfere with autoantigen adherence, activation of complement, recruitment of inflammatory cells (eg, eosinophils), and release of proteolytic enzymes, causing skin blistering and pruritus. IgG autoantibodies against BP180 and BP230 have been demonstrated to induce BP-like symptoms in animal models, and disease activity is associated with serum levels of anti-BP180 autoantibodies. 1,2

At this time, no therapies are specifically licensed for the treatment of patients with BP. The current standard of care for BP is treatment with topical corticosteroids (TCS) or OCS, either of which can be combined with conventional immunosuppressant therapy. Unfortunately, corticosteroid therapy in patients with BP typically causes comorbidities, which can be severe and even life-threatening, especially in older adults. As a result, patients with BP have a higher mortality rate than their peers, even when their disease is being treated. Alternative therapies targeting IgG (eg, IV administration of immunoglobulin [IVIg], plasma exchange, or protein A immunoadsorption) or biologics (eg, rituximab, omalizumab) have shown potential in small numbers of patients with BP. However, the efficacy and safety of these treatments have not been assessed in registrational studies. 3,4,5

Efgartigimod, a neonatal crystallizable fragment receptor (FcRn) antagonist, blocks FcRn-mediated recycling of IgG, effectively reducing IgG levels, including IgG autoantibody levels. The formulation for subcutaneous (SC) administration of efgartigimod PH20 SC (efgartigimod coformulated with recombinant human hyaluronidase PH20 [rHuPH20]) represents a rational and innovative therapeutic approach to autoimmune diseases mediated by IgG autoantibodies, such as BP.

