5.2. Exclusion Criteria

Participants are excluded from the study if any of the following criteria apply:

- 1. Other forms of pemphigoid (including but not limited to pemphigoid gestationis, drug-induced BP that resolves after culprit-drug withdrawal, anti-p200 pemphigoid, mucous membrane pemphigoid, and cicatricial pemphigoid), or other AIBDs (including but not limited to epidermolysis bullosa acquisita, pemphigus vulgaris, and exfoliative erythroderma)
- 2. Received unstable dose of treatments known to cause or exacerbate BP (eg, angiotensin converting enzyme inhibitors, penicillamine, furosemide, phenacetin, dipeptidyl peptidase 4 inhibitor) for at least 4 weeks prior the baseline visit
- 3B. Use of BP treatments other than OCS, such as TCS, conventional immunosuppressants (eg, azathioprine, cyclophosphamide, methotrexate, mycophenolate mofetil), or dapsone, including the following:

- a. sulfasalazine, IVIg, subcutaneous administration of immunoglobulin (SCIg), immunoadsorption or plasma exchange within 8 weeks of the baseline visit
- b. tetracyclines with or without nicotinamide at doses higher than the recommended daily allowance (RDA)/dietary reference intake (DRI) within 2 weeks of the baseline visit
- c. any monoclonal antibody (including rituximab or another anti-CD20 biologic) within 6 months of the baseline visit
- d. complementary therapies—such as traditional Chinese medicines, herbs, or procedures (eg, acupuncture)—within 4 weeks (or 5 half-lives) of the baseline visit, if the investigator determines that such therapies may interfere with the study's efficacy assessments and/or potentially risk the safety of the participant
- 4. Known contraindication to OCS therapy
- 5C.Clinically significant active infection that is not sufficiently resolved before baseline in the investigator's opinion
- 6A.Positive COVID-19 test result at screening (testing performed if required per local regulations)
- 7A. Any other known autoimmune disease or any medical condition that, in the opinion of the investigator, would interfere with an accurate assessment of clinical symptoms of BP, prevent participants from complying with protocol requirements, or put the participant at undue risk

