6.8.2. Prohibited Medications and Therapy During the Study

The following medications or treatments are not permitted while the participant receives IMP:

- Any systemic treatment for BP (except concurrent OCS), including but not limited to immunosuppressants, IVIg, SCIg, immunoadsorption, anti-CD20 biologics, tetracyclines with or without nicotinamide, dapsone, and IV or IM corticosteroids
- TCS (use must be discontinued before baseline)
- Any other biologic agent or experimental/study IMP
- Live or live-attenuated vaccines
- Complementary therapies, including traditional Chinese medicines, herbs, or procedures (eg, acupuncture), as assessed by the investigator

As discussed in Section 6.8.3, some of these treatments can be administered as rescue therapy if the participant discontinues IMP.

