9. APPENDICES

9.1 Main Intercurrent Events (ICE)

9.1.1 Immunosuppressants or dapsone at therapeutic doses for at least 4 weeks in total in the last 12 weeks before Week 36

- · Azathioprine, at least 1 mg/kg/day
- Mycophenolate mofetil, at least 2 g/day
- Mycophenolate mofetil hydrochloride, at least 2 g/day
- Mycophenolic acid, at least 1000 mg/day
- Cyclophosphamide, at least 1 mg/kg/day, or IV pulse 500 mg/month
- Methotrexate (sodium), at least 5 mg/week (in Japan), whereas 10 mg/week in Europe
- Ciclosporine, at least 3 mg/kg/day
- Dapsone, at least 1 mg/kg/day
- Hydroxychloroquine sulfate, at least 400mg/day
- Thalidomide, at least 50mg/day

For NCOD, time-to-event analyses and endpoints that consider the period 'through Week 36' any episode of at least 4 weeks in total is to be considered as an ICE, even if not in the last 12 weeks before Week 36. For these analyses, use the end of the 4 weeks as start date of the ICE. For endpoints 'at Week 36', use the end of 4 weeks that fully fall in the last 12 weeks before Week 36 as start date of the ICE.

SGS	Statistical Analysis Plan	
ARGX-113-2009	Final and Interim Analysis	Final 4.0 of 04NOV2024

9.1.2 IVIg/SCIg at immunomodulating dose (≥1 g/kg/month) at any moment before Week 36

'Immunoglobulins NOS' or 'Immunoglobulin G Human' or 'Immunoglobulins' or 'Immunoglobulin Human Normal' or 'Anti-D Immunoglobulin' and cmroute='INTRAVENOUS' or 'SUBCUTANEOUS'.

9.1.3 Immunoadsorption or plasma exchange (at least 1 procedure) at any moment before Week 36

• 'Plasmapheresis' or 'Immunoadsorption therapy' as PRDECOD, at least one cycle

9.1.4 Rituximab or other anti-CD20 biologics (at least 1 infusion) at any moment before Week 36

- Rituximab (PVVR, ARRX, ABBS), at least one cycle of 1 g or 375 mg/m²
- Obinutuzumab
- Ofatumumab
- Ocrelizumab
- Ibritumomab tiuxetan
- Veltuzumab
- Tocilizumab

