9.1.5 IV or IM corticosteroids

- administered (at least 1 administration, any dose) during the period from Week 28 to Week 36 (i.e., during the 8 week period required in the protocol to confirm the CRoff status)
 - or administered at any moment before Week 28 in any of the three following situations:
 - a) more than 60 mg/day of prednisone equivalent for 3 consecutive days (prednisone equivalent dose)
 - b) more than 40 mg/day of prednisone equivalent for 4 consecutive days (prednisone equivalent dose)
 - c) more than 7 days in total

SGS	Statistical Analysis Plan	
ARGX-113-2009	Final and Interim Analysis	Final 4.0 of 04NOV2024

 medications with ATC level2 = 'CORTICOSTEROIDS FOR SYSTEMIC USE' and cmroute='INTRAVENOUS' or 'INTRAMUSCULAR'

For NCOD, time-to-event analyses and endpoints that consider the period 'through Week 36' any administration of this type of medication is to be considered as an ICE, even if not during the period from Week 28 to Week 36. For these analyses, use the first day of the medication as start date of the ICE. For endpoints 'at Week 36', use the end of the 3, 4 or 8 (more than 7) days as start date of the ICE for situations a), b) and c) respectively.

9.1.6 Tetracyclines administered at least 100 mg/day for at least 2 weeks in total in the last 10 weeks before Week 36

medications with ATC level4 = 'TETRACYCLINES'

[figure not shown]
For NCOD, time-to-event analyses and endpoints that consider the period 'through Week 36' any episode of at least 2 weeks in total is to be considered as an ICE, even if not in the last 10 weeks before Week 36. For these analyses, use the end of the 2 weeks as start date of the ICE. For endpoints 'at Week 36', use the end of 2 weeks that fully fall in the last 10 weeks before Week 36 as start date of the ICE.

9.1.7 Any interventional study drug under development for BP given at any moment before Week 36

medications will be evaluated during the course of the study

9.1.8 Very potent TCS for 7 consecutive days or 14 days in total given at any moment before Week 36

• medications with ATC level4 = 'CORTICOSTEROIDS, VERY POTENT (GROUP IV)' and cmroute = 'TOPICAL' Use the end of the 7 or 14 days as start date of the ICE.

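### The biologic intercurrent-event item stops at anti-CD20 agents, so a participant given another biologic for BP, such as omalizumab, can be scored as a responder

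*Protocol*

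**What the plan says.** Four parts of the plan deal with biologic drugs, and their scope differs.

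- **Eligibility.** Protocol 5.2, criterion 3B(c), excludes, among BP treatments other than OCS, "any monoclonal antibody (including rituximab or another anti-CD20 biologic) within 6 months of the baseline visit".
- **Conduct.** Protocol 6.8.2 prohibits, while the participant receives IMP, "Any other biologic agent or experimental/study IMP".
- **Background.** Protocol 2.1 says that "biologics (eg, rituximab, omalizumab) have shown potential in small numbers of patients with BP". Section 2.2 again lists omalizumab among adjuvant treatments that have been evaluated.
- **Analysis.** In protocol 9.3.2 the biologic item among the main intercurrent events (1d) is "Rituximab or anti-CD20 biologic, at least 1 infusion". SAP 3.4.2 and 4.1.2.1 carry it over, and SAP 9.1.4 implements it under the title "Rituximab or other anti-CD20 biologics (at least 1 infusion) at any moment before Week 36".

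A further item, 1g, covers "Any interventional study drugs under development for BP". SAP 9.1.7 attaches no drug list to it and says only that "medications will be evaluated during the course of the study".

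Under the composite strategy, a listed intercurrent treatment makes the participant a nonresponder. SAP 4.1.2.2 does the same for rescue therapy before week 36.

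**The concern.** The protocol treats every monoclonal antibody as relevant BP treatment at entry and every other biologic as prohibited on IMP, but its nonresponse rule reaches only one class. If a participant receives omalizumab for BP and is in complete remission off OCS at week 36, the remission can be credited to the assigned arm although another drug may have produced it. The composite strategy exists to prevent that.

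The same event list governs three key secondary endpoints handled by the composite strategy: IGA-BP 0 off OCS, CDA without relapse, and CR on minimal OCS. It also sets the point at which OCS dose stops accumulating for NCOD (SAP 4.1.3.1). If the drug is not an event, later low-steroid days on IMP stay in that participant's NCOD. The itch endpoint is unaffected, because it ignores intercurrent events.

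**Working it through.** **1. The lists side by side**

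| Place | Biologics covered |
|---|---|
| Protocol 5.2, 3B(c) | Any monoclonal antibody |
| Protocol 6.8.2 | Any other biologic, while on IMP |
| Protocol 9.3.2 item 1d; SAP 3.4.2 and 4.1.2.1 | Rituximab and anti-CD20 agents |
| SAP 9.1.4, named drugs | Rituximab, obinutuzumab, ofatumumab, ocrelizumab, ibritumomab tiuxetan, veltuzumab, tocilizumab |

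Omalizumab appears in none of the analysis lists. Tocilizumab appears under a label that does not describe it.

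**2. One participant traced through the rules**

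Suppose omalizumab is given for BP after a first relapse, with IMP continuing. The possible routes to nonresponse on the primary endpoint are:

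- *Listed treatment:* not under 1d; under 1g only if judged a study drug under development for BP.
- *IMP stopped for lack of efficacy:* not automatic. Section 6.8.3 requires a second relapse, and taking a prohibited drug is not itself a trigger in 7.1.1.
- *Rescue:* only if recorded as such. The rescue lists in protocol 6.8.3 and SAP 3.4.2 name no biologic, though the wording is open-ended.
- *Death or missing data:* not applicable.

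If the participant is then in remission off OCS for at least 8 weeks at week 36, the full analysis set scores a response. The treatment-policy supplementary analysis also counts it, since it disregards intercurrent events. Only the per-protocol sensitivity analysis might remove the participant. This participant would already fail the CDA-without-relapse endpoint; for that endpoint the gap needs someone who has not relapsed.

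There is a second route. SAP 4.1 treats an IMP stop for an adverse event as still receiving IMP, while the prohibition in 6.8.2 applies only during IMP. A biologic given for BP after such a stop, and not recorded as rescue, leads to the same result. It does not affect NCOD, which covers only the on-IMP period.

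**3. How narrow the route is**

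Off OCS for 8 weeks at week 36 means a last dose by about week 36 − 8 = week 28. Protocol 6.8.1.3 and Table 7 require 2 weeks of sustained CDA, then 4 to 7 dose levels below 0.5 mg/kg/day (depending on weight) of at least 2 weeks each. That is 2 + 8 = 10 to 2 + 14 = 16 weeks, so an uninterrupted taper must rest on CDA from about week 12 to week 18. Treatment failure is declared after at most about 3 + 3 + 1 = 7 weeks without CDA.

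**4. Illustrative size**

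The protocol's design rates are redacted. The SAP 1.4.2.1 simulation rates (20% placebo, 50% efgartigimod) are used as an assumption, with n = 60 per arm and two-sided 5%:

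power = Φ{ [d − 1.96·√(2p̄(1−p̄)/n)] / √[(p₁(1−p₁)+p₂(1−p₂))/n] }

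With d = 0.30 and p̄ = 0.35: (0.300 − 0.1707)/0.0827 = 1.56, so power is 94.1% (Fisher exact: 91.3%). This is consistent with the protocol's claim of more than 90% with 120 participants.

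Each misclassified participant adds 1/60 = 1.7 points to that arm's rate.

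| Cases | Placebo rate if all in placebo | Power | Crude odds ratio | Crude odds ratio if all in the efgartigimod arm |
|---|---|---|---|---|
| 0 | 12/60 = 20.0% | 94.1% | 4.00 | 4.00 |
| 1 | 13/60 = 21.7% | 90.9% | (30/30)/(13/47) = 3.62 | (31/29)/(12/48) = 4.28 |
| 2 | 14/60 = 23.3% | 86.7% | (30/30)/(14/46) = 3.29 | (32/28)/(12/48) = 4.57 |
| 3 | 15/60 = 25.0% | 81.6% | (30/30)/(15/45) = 3.00 | (33/27)/(12/48) = 4.89 |

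Three cases in each arm would lower power only to 92.8%.

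**The case against.** The strongest reply is that other rules already catch the participants most likely to be given an extra drug. Failure to reach CDA stops IMP and is nonresponse (protocol 6.8.1.3). A second relapse or steroid toxicity stops IMP and opens rescue (6.8.3), and all rescue before week 36 is nonresponse. Stopping IMP for lack of efficacy is itself an event. This stands, and with the timing above it makes the route narrow.

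It can also be said that entry and event lists need not match. Section 4.2.2 bases the wash-out durations on pharmacokinetics, while SAP 3.4.2 lists therapies that may influence efficacy. So the difference is not a contradiction in itself. But pharmacokinetics explains how long the wash-out lasts, not why the class counts as BP treatment, and 6.8.2 bars the same drugs on IMP. SAP 3.4.2 also counts a listed therapy as an event when its dose or duration is unknown, so a deliberate exemption for other antibodies would be out of character.

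Item 1g may catch some biologics, but without a prespecified list it leaves the decision to case-by-case judgement. The per-protocol analysis is a sensitivity analysis and does not repair the primary one.

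A reader might infer that sulfasalazine has the same gap, since 3B(a) excludes "sulfasalazine, IVIg, subcutaneous administration of immunoglobulin (SCIg), immunoadsorption or plasma exchange within 8 weeks of the baseline visit" and SAP 9.1.1 omits sulfasalazine. The documents do not support giving it equal weight: they say nothing about its efficacy in BP and supply no dose threshold, which most SAP 9.1.1 entries carry.

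**Conclusion.** The gap is real but narrow. A biologic outside the SAP 9.1.4 list, given for BP before week 36, can precede a scored response when three conditions hold together: it is not recorded as rescue, it is not captured under item 1g, and IMP was not stopped for lack of efficacy.

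Three stronger readings are tempting and not supported:

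- *That anti-CD20 agents are the only biologics that can count.* Tocilizumab is listed in SAP 9.1.4, and item 1g may reach others.
- *That the bias runs towards no difference because such use falls mostly on placebo.* The documents give neither the number nor the arm of cases. Cases in the efgartigimod arm would inflate the effect.
- *That omalizumab is presented as an established BP treatment.* Section 2.1 claims only potential in small numbers of patients, and section 2.2 groups it with adjuvants that have had various shortcomings.

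The power and odds-ratio figures rest on the SAP's simulation rates and on case counts assumed for illustration. They show sensitivity per case and do not estimate a likely loss. The reason to act is that the definition can be settled now at almost no cost, whereas settling it after a case has been seen by treatment arm would be open to challenge.

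**What to change.** Before unblinding, and decided by staff who have not seen unblinded data:

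- Reword item 1d (protocol 9.3.2; SAP 3.4.2, 4.1.2.1, 9.1.4) as: *any monoclonal antibody or other biologic given for BP, other than the assigned IMP, at least 1 administration before week 36*. The IMP exception is needed because protocol Table 5 types efgartigimod as a biologic; without it, every treated efgartigimod participant would literally qualify.
- Name omalizumab alongside the anti-CD20 agents in SAP 9.1.4, and move tocilizumab out from under the anti-CD20 description.
- State that IVIg and SCIg stay under their own item and dose threshold (SAP 9.1.2), so that the wider wording does not override it.
- Record the change in SAP 6.1, which already documents other departures from the protocol's event definitions.
- Leave sulfasalazine to the sponsor, who can reconcile SAP 9.1.1 with exclusion 3B(a) if wanted.

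The cost is SAP wording and a few drug codes. No new data are needed: the reason for use is recorded on the eCRF (protocol 6.8), and therapies are coded with WHO-DD and ATC (SAP 3.4.1). The downside is that an occasional participant is reclassified as a nonresponder.
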